5.5. Justification for Dose and Dose Escalation Regimen

The investigational dulaglutide doses (3.0 mg and 4.5 mg) were selected considering adequate separation in PK exposure range between the doses and 1.5 mg to enable evaluation of their efficacy and adverse effect profiles. Ratios of mean area under concentration-time curve (AUC) for 3.0 mg/4.5 mg doses to 1.5 mg dose are 2.26 and 3.10, respectively. The steady-state mean AUC and 90% confidence intervals (CIs) for the 1.5 mg, 3.0 mg, and 4.5 mg doses are 11,800 (5300, 21,300), 26,700 (15,300, 41,400), and 36,600 (21,100, 56,500) ng.h/mL, respectively. Therefore, the ratio of mean AUC for 4.5 mg to 3.0 mg is anticipated to be 1.37. Based on predicted plasma exposures in patients with T2D receiving the highest investigational dulaglutide dose of 4.5 mg, the margins of safety (ie, plasma exposure multiples at the no-observed-adverse-effect level [NOAEL]) in chronic toxicology studies in monkeys and rats were 162-fold and 55-fold, respectively.

Data from Phase 2 Study GBGJ provided evidence for incremental efficacy of dulaglutide 3.0 mg and 4.5 mg once weekly versus 1.5 mg once weekly on glycemic control and body weight reduction. After 18 weeks of treatment (analysis of on-treatment data without rescue), the estimated treatment differences in HbA1c reduction with 3.0 mg and 4.5 mg once weekly relative to 1.5 mg once weekly were -0.22% and -0.26%, respectively. Larger differences were observed in subgroups of patients with higher baseline HbA1c (ie, $\geq 8.5\%$ [69 mmol/mol] vs. $< 8.5\%$ [69 mmol/mol]). Dulaglutide 3.0 mg and 4.5 mg once weekly also provided for additional body weight reduction over the 1.5 mg dose that exceeded 1 kg at Week 18, with further weight reduction expected with longer durations of treatment. Although the effects of dulaglutide 4.5 mg were generally greater than the effects of the 3.0 mg dose on measures of glycemic control and body weight, a larger study is required to fully characterize the benefit/risk profile of each higher dulaglutide dose compared with the 1.5 mg dose over a longer duration of treatment.

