7.7.5.3. Management of Patients with Severe, Persistent Hyperglycemia during the Treatment Period

Investigators will be trained on the application of criteria for deciding when and how to intervene in patients who do not reach glycemic targets. An additional therapeutic intervention should be considered in patients who develop severe, persistent hyperglycemia after randomization based on the following criteria:

- a) During the first 8 weeks postrandomization (up to Visit 5): An average FPG above 270 mg/dL (15.0 mmol/L) over at least a 2-week period (at least 4 values/week must be available)

OR

- b) Between Week 8 and Week 18 (between Visits 5 and 7): An average FPG above 240 mg/dL (13.3 mmol/L) over at least a 2-week period (at least 4 values/week must be available)

OR

- c) Between Week 18 and Week 26 (between Visits 7 and 8): An average FPG above 200 mg/dL (11.1 mmol/L) over at least a 2-week period (at least 4 values/week must be available) or HbA1c above 8.0% (64 mmol/mol)

OR

- d) Beginning at Week 26 (Visits 8 through 11): HbA1c above 8.0% (64.0 mmol/mol) which is not at least 0.3% less than the HbA1c at the previous scheduled measurement

Persistent hyperglycemia considered of severe intensity by the investigator should be reported on the AE eCRF whenever any of the above criteria are met.

In considering whether initiation of rescue therapy is warranted, investigators should first confirm that the patient is fully compliant with the assigned therapeutic regimen and that he/she does not have an acute condition causing severe hyperglycemia. If confirmed, the investigator will initiate an appropriate glucose-lowering intervention (rescue intervention) according to the guidance outlined in Section 7.7.1, and it will be recorded on the eCRF specified for collecting antihyperglycemic medications. Other GLP-1 RAs (including commercial Trulicity) or DPP-4 inhibitors must not be used as the rescue intervention. Patients who receive rescue intervention for hyperglycemia management should also continue administering study drug for the remaining period in the trial.

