9.2. Adverse Events

Investigators are responsible for monitoring the safety of patients who have entered this study and for alerting Lilly or its designee to any event that seems unusual, even if this event may be considered an unanticipated benefit to the patient.

The investigator is responsible for the appropriate medical care of patients during the study.

Investigators must document their review of each laboratory safety report.

The investigator remains responsible for following, through an appropriate health care option, AEs that are serious or otherwise medically important, considered related to the investigational product or the study, or that caused the patient to discontinue the investigational product before completing the study. The patient should be followed until the event resolves, stabilizes with appropriate diagnostic evaluation, or is reasonably explained. The frequency of follow-up evaluations of the AE is left to the discretion of the investigator.

Lack of drug effect is not an AE in clinical studies, because the purpose of the clinical study is to establish treatment effect.

After the informed consent form (ICF) is signed, study site personnel will record via eCRF the occurrence and nature of each patient's preexisting conditions, including clinically significant signs and symptoms of the disease under treatment in the study. In addition, site personnel will record any change in the condition(s) and any new conditions as AEs. Investigators should record their assessment of the potential relatedness of each AE to study procedure, investigational product, and study device via eCRF.

The investigator will interpret and document whether or not an AE has a reasonable possibility of being related to study treatment, study device, or a study procedure, taking into account the disease, concomitant treatment, or pathologies.

A "reasonable possibility" means that there is a cause and effect relationship between the investigational product, study device, and/or study procedure and the AE.

The investigator answers yes/no when making this assessment.

Planned surgeries and nonsurgical interventions should not be reported as AEs unless the underlying medical condition has worsened during the course of the study.

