Severe, persistent hyperglycemia will be collected as an AE during the trial to assess the risk of extreme imbalance in glycemic control, as defined in Section 7.7.5.3. Details of antihyperglycemic medication initiated as rescue therapy for severe, persistent hyperglycemia per these criteria will be collected on the antihyperglycemic concomitant therapy eCRF.

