10.1. Sample Size Determination

Assuming a screen failure rate of 40%, approximately 3000 patients will need to be screened to attain approximately 1800 patients randomized to the 3 treatment groups (600 patients/groups) in a 1:1:1 ratio for dulaglutide 4.5 mg, 3.0 mg, and 1.5 mg. Assuming 15% dropout, this will result in approximately 510 patients per arm completing 36 weeks of treatment (the primary time point).

The aforementioned sample size provides $\geq 80\%$ power to demonstrate superiority of at least 1 of the investigational dulaglutide doses (4.5 mg or 3.0 mg) to dulaglutide 1.5 mg with respect to the primary endpoint (change from baseline in HbA1c) at Week 36. This sample size is calculated based on the assumption that there is a treatment difference (for either investigational dose) in HbA1c change from baseline of approximately -0.22%, a standard deviation (SD) of 1.1%, and a 2-sided alpha of 0.05.

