6.10.1. Adverse Events

Summary statistics will be provided for the following data: medical history and/or preexisting condition AEs, TEAEs, treatment-emergent AESIs, and study and/or treatment discontinuations due to AEs or death. The numbers and proportions of patients experiencing each corresponding AE will be reported by treatment.

For each patient, the primary AE analysis will be summarized up to the end of the treatment period or premature termination of the study, whichever comes first.

As supportive analyses, SAEs, TEAEs, and treatment-emergent AESIs for each patient will be summarized through the end of the study, including the Safety Follow-up Period.

The incidence of patients with at least 1 TEAE will be summarized by PT and by treatment group, and also by the SOC and PT.

A summary of TEAEs by maximum severity will be presented descriptively by treatment group.

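### The protocol does not settle when meeting a rescue criterion is an adverse event; on a criteria-only reading, glycemic failure enters the any-TEAE count most often on 1.5 mg and attenuates an excess on the higher doses

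*Protocol*

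**What the plan says.** Three protocol statements bear on whether meeting a rescue criterion is an AE.

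- Section 9.2.2.2: "Severe, persistent hyperglycemia will be collected as an AE during the trial to assess the risk of extreme imbalance in glycemic control". It refers to Section 7.7.5.3 for the definition and does not itself mention a severity judgement.
- Section 7.7.5.3, after listing the glucose and HbA1c criteria: "Persistent hyperglycemia considered of severe intensity by the investigator should be reported on the AE eCRF whenever any of the above criteria are met". This requires a criterion and a judgement of severe intensity.
- Section 9.2: "Lack of drug effect is not an AE in clinical studies". No exception is given for rescue criteria.

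The criteria change over time. From Week 26 the criterion is an HbA1c above 8.0% "which is not at least 0.3% less than the HbA1c at the previous scheduled measurement". The entry range in Protocol 6.1 is 7.5-11.0%.

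TEAE incidence is a secondary safety endpoint for each higher dose against 1.5 mg (Protocol Table GBGL.1), and the synopsis plans Fisher's exact test on AE proportions. SAP 6.10 defines a TEAE as a new event or a preexisting condition that worsened, judged by maximum severity before and after baseline within a MedDRA term. SAP 6.2 keeps post-rescue data in safety analyses. In SAP 6.10.1, "The incidence of patients with at least 1 TEAE will be summarized by PT and by treatment group", with further tables by SOC and PT and by maximum severity. No TEAE total is planned without hyperglycemia terms.

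**The concern.** Meeting the HbA1c criterion is largely a failure of efficacy, and the trial's hypothesis is that this happens more often on 1.5 mg than on either higher dose. If those cases are also TEAEs, the comparator's any-TEAE rate rises more than the others. A real excess of side effects on 3.0 or 4.5 mg then looks smaller in the pooled total. The direction of the bias favours the doses for which approval is sought.

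The example of a patient who enters at 9.5% and sits at 8.3% at Week 36 shows the difficulty. Glycemia has improved, a rescue criterion may be met, and the documents do not say whether this is an AE or, if it is, whether it is treatment-emergent.

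**Working it through.** **1. The plan's own figure.** The sample size rests on a difference "in HbA1c change from baseline of approximately -0.22%, a standard deviation (SD) of 1.1%, and a 2-sided alpha of 0.05", and on "Assuming 15% dropout, this will result in approximately 510 patients per arm completing 36 weeks of treatment". The standard error is 1.1 × √(2/510) = 0.0689, and 0.22/0.0689 = 3.19. Power per comparison is Φ(3.19 − 1.96) = 89.1% at 0.05 and 83.0% at 0.025. For at least one dose at 0.025 each (both effective, correlation 0.5) it is 93.1%. The stated ≥80% is met. This step only fixes the effect size and SD; the documents give no TEAE or rescue rates.

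**2. Share above 8.0% at one visit.** From the documents: the Phase 2 differences "relative to 1.5 mg once weekly were -0.22% and -0.26%, respectively" for 3.0 and 4.5 mg, and SD 1.1%. Assumed: mean on-treatment HbA1c on 1.5 mg (m) of 6.6-7.5%, SD of the HbA1c level (s) of 0.9-1.1 (the plan's 1.1 is for change), and normality. The 0.3-point clause is ignored here. With d the difference:

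q(1.5) = P(Z > (8.0 − m)/s), q(high) = P(Z > (8.0 − m + d)/s).

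| m | s | d | 1.5 mg | higher dose | gap, points | 1.5 mg share of cases |
|---|---|---|---|---|---|---|
| 6.6 | 0.9 | 0.22 | 6.0% | 3.6% | 2.4 | 46% |
| 6.6 | 0.9 | 0.26 | 6.0% | 3.3% | 2.7 | 48% |
| 7.0 | 1.1 | 0.22 | 18.2% | 13.4% | 4.8 | 40% |
| 7.5 | 0.9 | 0.26 | 28.9% | 19.9% | 9.0 | 42% |
| 7.5 | 1.1 | 0.22 | 32.5% | 25.6% | 6.8 | 39% |

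The share is q(1.5)/[q(1.5) + 2q(high)], with d applied to both higher doses. It would be 33% with no dose effect. Simulating the Week 26/36/52 rule with the 0.3-point clause (m of 6.8-7.5%, within-patient correlation 0.85, both assumed) gives 22-46% on 1.5 mg and 17-38% on a higher dose, with 38-40% of cases on 1.5 mg.

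**3. Effect on any-TEAE.** If t is the rate of other TEAEs, every case is reported and counted, and the two are independent, then any-TEAE = t + (1 − t)q. With equal t in both arms the shift is (1 − t) × gap. For t of 50-70% (assumed), it runs from 0.30 × 2.4 = 0.7 points to 0.50 × 9.0 = 4.5 points. The repeated-visit gaps of 5.4-8.0 points give 1.6-4.0, inside that range.

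**4. A true excess.** Other TEAEs at 60% on 1.5 mg against 68% on a higher dose (assumed), 600 per arm, two-sided 0.05, normal approximation:

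| Criterion rates, 1.5 mg / higher | Any-TEAE, 1.5 mg / higher | Observed excess, points | Power |
|---|---|---|---|
| none counted | 60.0% / 68.0% | 8.0 | 82% |
| 5% / 3% | 62.0% / 69.0% | 7.0 | 72% |
| 10% / 6.6% | 64.0% / 70.1% | 6.1 | 62% |
| 18% / 13% | 67.2% / 72.2% | 5.0 | 46% |
| 33% / 25% | 73.2% / 76.0% | 2.8 | 20% |

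**5. Why these are upper bounds.** A separate simulation applied the Week 26 criterion at Weeks 26 and 36 (assumed mean baseline 8.5-8.8%, mean change on 1.5 mg −1.2 to −1.5, SD of change 1.1). Between 52% and 74% of patients meeting the criterion were below their own baseline HbA1c. Take assumed other-TEAE rates of 55% and 60% and criterion rates of 20% and 15%. If all cases count, the totals are 0.55 + 0.45 × 0.20 = 64.0% and 0.60 + 0.40 × 0.15 = 66.0%, leaving 2.0 of the 5 points. With 30% and 24% they are 68.5% and 69.6%, leaving 1.1. If only the 26-48% not below baseline counted, equally in both arms, 3.1-4.2 points would remain.

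**The case against.** The best reply is that the statements can be read together. Section 9.2.2.2 points to Section 7.7.5.3, which contains the severity judgement, and a specific provision can override the general sentence in Section 9.2. That reading is reasonable and would sharply reduce the number of cases. But Section 7.7.5.3 also introduces its numeric criteria as the basis for identifying severe, persistent hyperglycemia, so the text does not settle whether the definition cited is the numbers or the numbers plus the judgement.

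A second reply is that a patient below baseline has neither a new nor a worsened condition. This may hold, but SAP 6.10 decides by recorded severity within a MedDRA term. A case with no preexisting hyperglycemia term, or with one recorded at lower severity, could still count.

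A reader might infer two stronger things that the documents do not support.

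- *That the cases fall mostly in the 1.5 mg arm.* That arm has the highest rate, but under half of the cases in every scenario above.
- *That side effects would be masked.* Hyperglycemia has its own PT row. GI events are analysed separately (SAP 6.10.1.3), SAEs are listed by PT (6.10.1.1), and treatment discontinuation due to AEs has its own curves and log-rank test (6.3). Rescued patients are to stay on study drug. None of these comparisons is diluted, and any-TEAE is outside the Type 1 error scheme.

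Nor does differing practice between sites bias the arms by itself: assignment is randomized and double-blind, so site habits balance in expectation. The bias comes from the efficacy difference.

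The separate summary in SAP 6.10.1.2.2.2 does not repair the total. It covers rescue starts rather than hyperglycemia AEs, and only if at least 1% are rescued. PT rows cannot be subtracted to rebuild a patient-level total, because patients overlap.

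**Conclusion.** The reporting rules are inconsistent, and the SAP has no TEAE total that is insensitive to how the inconsistency is resolved in practice. If cases are reported on the criteria alone, the any-TEAE and maximum-severity comparisons are biased toward the higher doses. The effect is attenuation of a pooled count: 0.7-4.5 points when true rates are equal, as an upper bound.

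The direction follows from the trial's own effect size. The magnitude depends on HbA1c levels, other-TEAE rates, independence, full reporting and full counting as treatment-emergent, none of which the documents give. Substantial loss of a true excess needs high criterion rates together with a modest excess.

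**What to change.** 1. Reconcile Protocol 7.7.5.3, 9.2 and 9.2.2.2 into one rule on which cases meeting a criterion go on the AE form. This concerns AE reporting only; rescue thresholds and patient management stay as they are.
2. State in SAP 6.10 how a reported case with HbA1c above 8.0% but below the patient's baseline is treated under the TEAE definition.
3. In SAP 6.10.1, add any-TEAE and maximum-severity summaries by arm without hyperglycemia terms, beside the planned ones and labelled as a sensitivity presentation. They should not replace the planned total, since genuine hyperglycemic events would drop out too.

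The cost is a clarification to sites, a sentence in the SAP, and extra summaries from data already collected. The downside is two TEAE totals to explain. Item 3 remains useful even if some cases have been reported before the rule is clarified.

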9.2.2.3. Pancreatitis

Acute pancreatitis is defined as an AE of interest in all trials with dulaglutide, including this trial. Acute pancreatitis is an acute inflammatory process of the pancreas that may also involve peripancreatic tissues and/or remote organ systems (Banks and Freeman 2006). The diagnosis of acute pancreatitis requires 2 of the following 3 features:

- abdominal pain, characteristic of acute pancreatitis (generally located in the epigastrium and radiates to the back in approximately half the cases [Banks and Freeman 2006; Koizumi et al. 2006]; the pain is often associated with nausea and vomiting);
- serum amylase (total and/or pancreatic) and/or lipase $\geq 3 \times$ ULN
- characteristic findings of acute pancreatitis on computed tomography (CT) scan or magnetic resonance imaging (MRI).

If acute pancreatitis is suspected, appropriate laboratory tests (including levels of pancreatic amylase and lipase) should be obtained via the central laboratory (and locally, if needed). Imaging studies, such as abdominal CT scan with or without contrast, MRI, or gallbladder ultrasound, should be performed. If laboratory values and/or abdominal imaging support the diagnosis of acute pancreatitis, the patient must discontinue therapy with investigational product, but will continue in the study on another glucose-lowering regimen (see Section 7.7.1 and Section 8.1.1 for details on the introduction of new antihyperglycemic interventions). A review

of the patient's concomitant medications should be conducted to assess any potential causal relationship with pancreatitis.

Each suspected case of AE of pancreatitis must be reported. If typical signs and/or symptoms of pancreatitis are present and confirmed by laboratory values (lipase or amylase [total and/or pancreatic]) and imaging studies, the event must be reported as an SAE. For a potential case that does not meet all of these criteria, it is up to the investigator to determine the seriousness of the case (AE or SAE) and the relatedness of the event to study drug.

Each patient will have measurements of p-amylase and lipase (assessed at the central laboratory) as shown on the Schedule of Activities (Section 2) to assess the effects of the investigational doses of dulaglutide on pancreatic enzyme levels. Serial measures of pancreatic enzymes have limited clinical value for predicting episodes of acute pancreatitis in asymptomatic patients (Nauck et al. 2017; Steinberg et al. 2017a; Steinberg et al. 2017b). Thus, further diagnostic follow-up of cases of asymptomatic pancreatic hyperenzymemia (lipase and/or pancreatic amylase $\geq 3 \times \text{ULN}$) is not mandated, but may be performed based on the investigator's clinical judgement and assessment of the patient's overall clinical condition. Only cases of pancreatic hyperenzymemia that undergo additional diagnostic follow-up and/or are accompanied by symptoms suggestive of pancreatitis will be submitted for adjudication.

All suspected cases of acute or chronic pancreatitis will be adjudicated by an independent CEC. In addition, AEs of severe or serious abdominal pain of unknown etiology will also be submitted to the adjudication committee to assess for possible pancreatitis or other pancreatic disease. Relevant data from patients with acute or chronic pancreatitis and those with severe or serious abdominal pain will be entered into a specifically designed eCRF page by study site or Lilly staff. The adjudication committee representative will enter the results of adjudication in a corresponding eCRF page.

9.2.2.4. C-Cell Hyperplasia and C-Cell Neoplasms

Individuals with personal or family history of certain thyroid or nonthyroid endocrine abnormalities or certain preexisting laboratory and genetic characteristics will be excluded from the study (see Section 6.2). Patients with a personal or family history of MTC or personal history of multiple endocrine neoplasia syndrome type 2, or who have serum calcitonin ≥ 20 ng/L at study entry as determined by the central laboratory will be excluded. The assessment of thyroid safety during the trial will include reporting of thyroid treatment-emergent (TE) AEs (TEAEs) and measurements of calcitonin according to the Schedule of Activities (Section 2).

Patients who develop serum calcitonin increases $\geq 50\%$ of the screening value AND an absolute value ≥ 20 ng/L and < 35 ng/L at a postrandomization visit will be asked to repeat the measurement within 1 month. If this repeat value is increasing ($\geq 10\%$ increase from the initial elevated value), the patient will be encouraged to undergo additional endocrine assessment and longer-term follow-up by an endocrinologist to rule out a serious adverse effect on the gland.

Patients with an increase in serum calcitonin $\geq 50\%$ of the screening value AND an absolute value ≥ 35 ng/L at a postrandomization visit will be asked to immediately undergo additional endocrine assessments and longer-term follow-up by an endocrinologist.

For patients who require additional endocrine assessments due to increased calcitonin concentration per the criteria provided in this section or for thyroid-related TEAEs, data from the follow-up assessments will be collected on a specific eCRF.

9.2.2.5. Hypersensitivity Reactions

All hypersensitivity reactions will be reported by the investigator as either AEs or, if any serious criterion is met, as SAEs. Additional data about these events, such as type of reaction and treatment received, will be collected on an eCRF created for this purpose. Injection site reactions will be collected on an eCRF separate from the hypersensitivity reaction eCRF. At the time of AE occurrence, samples will be collected for measurement of dulaglutide anti-drug antibodies (ADA) and dulaglutide concentration. Study drug should be temporarily interrupted in any individual suspected of having a severe or serious hypersensitivity reaction to study drug (Section 8.1.2). Study drug may be restarted when/if it is safe to do so, in the opinion of the investigator. If study drug is permanently discontinued, see Section 8.1.1 for procedures required in this situation.

